#### **7.2.4. Specific Aim 3: To explore genetic, metabolic, and social/behavioral moderators of the efficacy of bupropion on cigarette abstinence and safety.**

These variables may either be continuous, or categorical, and we will address the aim by testing for moderation using the analytical models in Aim 1, testing for interactions with treatment. We will explore whether the risk of AEs and the efficacy of bupropion treatment (vs. placebo) is moderated by: 1) the rate of nicotine metabolism (i.e., NMR) and variation in *CYP2A6*; 2) the rate of bupropion metabolism (i.e., variation in *CYP2B6* and plasma concentrations of bupropion and hydroxybupropion); and 3) variation in social/behavioral variables, including weight concerns, body image, adverse childhood experiences, and the presence of other smokers in the home. Because this is exploratory, we will test at  $\alpha = 0.05$ , using the z-score for the interaction term for binary or continuous predictors, or the Wald  $\chi^2$  for categorical predictors.

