Statistical Methodology	
Preliminary analyses will assess sample characteristics (e.g., age, race, study site) by treatment using t-test or contingency table methods. These variables will also be examined for their relationship to completion of outcome assessments. Variables related to treatment arm or completion of follow ups will be included as covariates in analyses of study aims. Compliance measures will be evaluated across treatment arms, and controlled for in primary analyses. We will use intent-to-treat as the primary method to evaluate study aims. For Aim 1, we will test treatment group differences in a binary abstinence outcome that is a repeated measure using a generalized estimating equations (GEE) model with a logit link. Quit rates after 10 weeks of study medication and at 24 weeks post-TQD will represent our primary outcome variables. Medication group (bupropion vs. placebo) and time point (10 and 24 weeks) will be treated as categorical predictor variables, and the model will predict separate effects of treatment on abstinence at each time point (an interaction). Mean birth weight will be compared for treatment groups using a two-sample t-test, in the context of multiple linear regression. We will also compare treatment arms for equivalence of the frequency of moderate-to-severe adverse events (individual and total). For Aim 2, we will use a regression-based path model approach to examine mediation of treatment effects by changes in depression and craving scores, which will be entered in the model as standardized pre-post differences, continuously distributed and treated as normal in linear regression. The effects of treatment arm on mediators, and of mediators on outcome, will be assessed using linear regression and standardized variables. For Aim 3, we will explore whether the risk of adverse events and the efficacy of bupropion treatment (vs. placebo) is moderated by: 1) the rate of nicotine metabolism and variation in CYP2A6; 2) the rate of bupropion metabolism (i.e., variation in CYP2B6 and plasma concentrations of bupropion and hydroxybupropion); and 3) variation in social/behavioral variables, including weight concerns, body image, and the presence of other smokers in the home.

CONFIDENTIAL

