##### **Metabolic, Genetic, and Social/Behavioral Moderators of Bupropion's Efficacy.**

i. The rate of nicotine metabolism [i.e., the nicotine metabolic ratio (NMR)] is largely heritable (60-63) and several functional polymorphisms in the *CYP2A6* gene that affect enzyme activity have been characterized by [name], a consultant to this project (64-65). However, as-yet-unidentified variants in *CYP2A6* also account for heritability in nicotine clearance (63), the rate of which is also influenced by age, sex, hormonal factors, and smoking (65-66). A genetically informed biomarker, the NMR, is based on the measurement of two long-lasting nicotine metabolites and can overcome these genotype limitations. The NMR reflects *CYP2A6* activity and the influence of other genetic and environmental influence on nicotine clearance *in vivo* (66-68). The NMR can be assessed non-invasively (e.g., from saliva, urine, or plasma)

CONFIDENTIAL

without additional drug administration, using metabolite levels from nicotine derived from the smokers' usual cigarettes. Results are highly reproducible and independent of time since last cigarette (67). Lastly, the NMR is strongly correlated with nicotine clearance ( $r=.70-.95$ ), and *CYP2A6* genotypes, in smokers of European (68-71) and African ancestry (64, 72). Importantly, NMR has been associated with smoking cessation and response to therapy in independent clinical trials (73). Smokers characterized as slow metabolizers of nicotine (the lowest quartile of the NMR) have significantly higher quit rates on NRT than faster metabolizers (higher three quartiles of the NMR) (70, 74); the same is true in African American smokers (72). In an RCT of bupropion, slow metabolizers had high quit rates on placebo, which were not enhanced by bupropion. In contrast, fast metabolizers showed high quit rates only with bupropion (15). Thus, we will examine NMR as a moderator of treatment response on the hypothesis that slow metabolizers will do well on either placebo/counseling alone or bupropion, while fast metabolizers will achieve little benefit from counseling alone (i.e., placebo), but will respond well to bupropion. This has implications for personalizing smoking cessation treatment in pregnant women.

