ii. Variation in *CYP2B6*. Two studies from [name] group have also shown that a variant (*CYP2B6\*6*) in the gene encoding the cytochrome P450 enzyme 2B6 (which metabolizes bupropion to its major active metabolite, hydroxybupropion) moderated bupropion response. First, in a study of 326 Caucasian smokers (75), at the end of treatment and at 6-month follow up, carriers of the variant allele (45% of the sample) had significantly higher quit rates than placebo-treated subjects (32.5% vs. 14.3 and 31.2% vs. 12.9%, respectively). In the group with no variant alleles, bupropion treatment was no better than placebo in promoting abstinence. Second, in a 7-week treatment trial in 540 African-American light smokers (<11 CPD), 42.9% of bupropion-treated subjects were not adherent to treatment (20). In the 154 treatment-adherent bupropion subjects, higher hydroxybupropion (but not bupropion) concentrations resulted in higher rates of smoking cessation after 3, 7, and 26 weeks of treatment (ORs = 2.82, 2.96, and 2.37, respectively). Using alleles that have been shown to encode a reduced-function enzyme, [name] and colleagues found that the slow metabolizer group had significantly lower hydroxybupropion concentrations and both the slow metabolizer and intermediate groups had lower hydroxybupropion/bupropion ratios than faster metabolizers. Because 16% of African Americans and 6% of Caucasians are slow metabolizers, with the proportion of intermediate metabolizers in these groups being 48% and 38%, respectively, the potential for variation in *CYP2B6* to moderate treatment response is substantial. However, because of other influences on bupropion and hydroxybupropion concentrations (e.g., concomitant medications, hormone status, and bupropion adherence), there are inconsistent findings on the impact of *CYP2B6* variation on smoking cessation. In the present study, we will measure *CYP2B6* genotype, bupropion and hydroxybupropion concentrations, medication adherence, and enzymatic activity and the impact of these on the likelihood of smoking cessation (and risk of AEs).

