## **7.2. Statistical Analyses**

[name] will oversee analyses, which will be conducted using Stata, SAS, or R-Language software. Preliminary analyses will assess sample characteristics (e.g., dependence, race) by treatment using t-test or contingency table methods. These variables will also be examined for their relationship to completion of outcome assessments. Variables related to treatment arm or completion of follow ups will be included as covariates in analyses of study aims. Compliance measures will be evaluated across treatment arms, and controlled for in primary analyses. We will examine the correlation between self-report and pill count data and week-5 bupropion plasma levels. We will use intent-to-treat as the primary method to evaluate study aims.

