### **7.2.2. Specific Aim 1: To compare the efficacy of bupropion with placebo for smoking cessation in pregnant smokers.**

For **H1**, we will test for treatment group differences in a binary abstinence outcome that is a repeated measure using a generalized estimating equations (GEE) model with a logit link. Quit rates at the end of week 10 of treatment and 24 weeks post-TQD will represent our primary outcome variables. Medication group (bupropion vs. placebo) and time point (end of week 10 of treatment and 24 weeks post-TQD) will be treated as categorical predictor variables, and the model will predict separate effects of treatment on abstinence at each time point (an interaction). Our initial analyses will be stratified by site, and we will carefully examine the models for differences by site, testing for an overall interaction. We will use baseline depression (PHQ-9 score of 10) to stratify the randomization. The model may include a small number of covariates added to control error or adjust for confounding [e.g., age, history of pre-term delivery, baseline gestational age, daily smoking rate]. Any variables found to be associated with both outcome and treatment assignment will be entered as covariates. In the absence of an overall interaction (by site), we will pool the study population and account for site in the model as a binary predictor. To evaluate the effectiveness of randomization, we will compare summary statistics for participant characteristics in the two study arms. If there is an imbalance in participant characteristics, statistical adjustment will be used to ensure that the initial results were not biased by it.

Because many participants will fail to become completely abstinent, but may show a reduction in smoking, we will examine cigarette consumption as a secondary outcome. The analysis will be similar to the primary analysis, except that we examine the effect of treatment arm on daily cigarette counts using a GEE model with a negative-binomial link. Likewise, time to (recurrent) event models will be fitted using Cox regression, stratified by event sequence, as in Schnoll et al. (52), to assess lapse and recovery events over 24 weeks.

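### The CYP2B6-by-treatment moderation model in Section 7.2.4 prespecifies no race-by-treatment term, although the plan reports metaboliser frequencies that differ by ancestry

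*Combined protocol and SAP*

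**What the plan says.** Section 7.2.4 handles all moderators alike, by "testing for moderation using the analytical models in Aim 1, testing for interactions with treatment", each at the 0.05 level. It names no race or ancestry term, no race-by-treatment term and no analysis within ancestry groups. Section 7.1 calls this aim hypothesis generating and claims no power for it.

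The CYP2B6 paragraph of Section 1.1 gives metaboliser frequencies by ancestry: "Because 16% of African Americans and 6% of Caucasians are slow metabolizers". The intermediate group is also more common among African Americans, at 48% against 38%. The paragraph uses these figures to argue that moderation by the gene could be substantial. The paragraph on nicotine metabolism gives no such frequencies for CYP2A6. It says only that the nicotine metabolite ratio (NMR) tracks CYP2A6 genotype in smokers of European and of African ancestry.

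Race is named in the preliminary comparisons: "Preliminary analyses will assess sample characteristics (e.g., dependence, race) by treatment using t-test or contingency table methods" (Section 7.2; the Study Summary is similar). It could reach the aim models by four routes:

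- Section 7.2: if it is related to treatment arm or to completion of follow-up.
- Section 7.2.1: if it is associated with missing data at p < 0.05.
- Section 7.2.2: "Any variables found to be associated with both outcome and treatment assignment will be entered as covariates".
- Section 7.2.2: as one of a small number of optional covariates, whose examples are "e.g., age, history of pre-term delivery, baseline gestational age, daily smoking rate".

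Each route brings race in as a covariate. None brings in its interaction with treatment.

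**The concern.** Treatment arm is randomised; genotype is not. A genotype-by-treatment term compares the bupropion effect between groups of women who, on the plan's own frequencies, differ in ancestry and so in whatever goes with ancestry. If the bupropion effect varies along any of those lines, the genotype term absorbs part of the variation.

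The existing covariate rules do not deal with this. Randomisation means race will be associated with arm only by chance. Even when race does enter, a main effect adjusts the overall quit rate and leaves the treatment effect common across race. It is the difference in treatment effect that confounds the interaction.

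The aim exists to produce hypotheses about who responds to bupropion. Naming the gene when the source is something else would send the follow-up work in the wrong direction.

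**Working it through.** **Base model.** The plan gives no figure for Aim 3, so the only stated figure to reproduce is the week-10 power in Section 7.1.1 (88%), which concerns the Aim 1 comparison that Aim 3 builds on. Inputs: 180 per arm, quit rates 21.2% and 35.9%, two-sided 0.05.

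- Difference = 0.147; pooled rate = 0.2855.
- Null SE = √(2 × 0.2855 × 0.7145 / 180) = 0.0476.
- Alternative SE = √((0.212 × 0.788 + 0.359 × 0.641) / 180) = 0.0470.
- z = (0.147 − 1.96 × 0.0476) / 0.0470 = 1.14, so power is 87.3%, in line with 88%.

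**Ancestry by genotype group.** Call women who are neither slow nor intermediate *normal* metabolisers: 100 − 16 − 48 = 36% of African Americans and 100 − 6 − 38 = 56% of Caucasians. The mix is an assumption, here half and half.

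- African American share among slow = 16 / (16 + 6) = 72.7%.
- African American share among normal = 36 / (36 + 56) = 39.1%.

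At African American shares of 30% and 70%, the pairs are 53% versus 22% and 86% versus 60%.

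**Bias with no gene effect.** Assume treatment odds ratios of 1.5 in African Americans and 2.5 in Caucasians. The log odds ratio in each genotype group is roughly the mix-weighted average, so

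spurious ratio of odds ratios ≈ (1.5 / 2.5)^(0.727 − 0.391) = 0.84.

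With 1.2 and 2.5 it is (1.2 / 2.5)^0.336 = 0.78. Swapping the two ancestry groups inverts the ratio (1 / 0.84 ≈ 1.19).

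**Visibility at N = 360.** Slow versus normal is about 180 × 0.11 = 20 against 180 × 0.46 = 83 women per arm. With a 21.2% placebo quit rate, the standard error of the log ratio is 0.81, so a 95% interval spans a factor of exp(1.96 × 0.81) = 4.9 either way. The expected z is ln(0.84) / 0.81 ≈ −0.21. The rejection rate is P(Z > 1.96 − 0.21) + P(Z < −1.96 − 0.21) ≈ 0.040 + 0.015 = 5.5%.

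**Range.** A large-sample logistic model was fitted to the expected cell counts (ancestry × CYP2B6 group × arm), with no true gene effect and African American shares of 30-70%:

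| Treatment OR in the two groups | Spurious ratio, slow + intermediate vs normal | Spurious ratio, slow vs normal | Rejection rate |
|---|---|---|---|
| 1.0 vs 2.1 | 0.86-0.89 | 0.78-0.81 | 5.6-6.0% |
| 1.0 vs 3.0 | 0.81-0.85 | 0.69-0.73 | 6.3-7.3% |
| 1.0 vs 4.4 | 0.75-0.80 | 0.62-0.66 | 7.4-9.1% |

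**What removes the bias.** Take the half-and-half mix, odds ratios 1.0 vs 2.1, and slow + intermediate vs normal:

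- No race term: ratio 0.864.
- Race as a main effect: 0.863.
- Race and race-by-treatment: 1.00, with rejection back to 5.0%. The standard error goes from 0.493 to 0.506 (0.506 / 0.493 = 1.026).

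Across scenarios the standard error rises by about 2-5%.

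**The case against.** The strongest reply is that the premise is assumed. Bias needs a bupropion effect that differs by ancestry for reasons outside the gene, and the documents report none. The two CYP2B6 studies described in Section 1.1 were done in separate Caucasian and African American samples and show no ancestry difference in treatment effect. The mix is not given either. The aim is labelled exploratory, its intervals will be very wide, and under modest assumptions a false signal would arise about once more in every 100-200 tests. All of this stands and limits the weight of the point.

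It does not remove the point. Exploratory status explains the lack of power and of multiplicity control. It is not a reason to leave out a simple adjustment for a correlate of genotype that the plan itself documents.

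Four stronger readings are tempting, and the documents do not support them:

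- *The plan shows the same imbalance for CYP2A6.* It gives ancestry frequencies for CYP2B6 only.
- *Race is excluded from the models.* It is not; the conditional and discretionary routes are open. What is missing is its interaction with treatment.
- *The unadjusted 0.05 level makes this worse.* That is a separate multiplicity question and says nothing about ancestry.
- *The main efficacy result is affected.* The overall Aim 1 treatment comparison rests on randomised arms and does not depend on the genotype term.

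A reader might also take the paper on ancestry-informative markers in the reference list as a sign of planned adjustment. Nothing in the body text cites it.

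**Conclusion.** The point holds for CYP2B6, as a low-priority improvement. The planned interaction model is open to confounding by ancestry, and the routes by which race could enter would not correct it.

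The size is conditional. With a half-and-half mix and odds ratios of 1.5 and 2.5, the spurious ratio is about 0.84 for slow versus normal metabolisers and the rejection rate about 5.5%. Reaching 7.4-9.1% takes odds ratios as far apart as 1.0 and 4.4. The calculation treats every participant as African American or Caucasian and applies the Section 1.1 frequencies to this population; both are assumptions. The cost to the trial is therefore a biased estimate and possible misattribution, not a serious loss of type I error control. For CYP2A6 and NMR the same mechanism is possible, but the plan's figures do not establish it.

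**What to change.** In Section 7.2.4, prespecify that the CYP2B6 moderation model includes self-reported race and race-by-treatment. Because the Aim 1 abstinence model estimates a separate treatment effect at week 10 and at week 24 post-TQD, the race-by-treatment term should be allowed at each time point. At a minimum, report this as a sensitivity model beside the unadjusted one. Apply the same rule to CYP2A6 and NMR, stated as a precaution.

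Label any genotype results within race groups as descriptive. Under the half-and-half mix, 6% of 180 is about 11 Caucasian slow metabolisers, or 5 per arm. At a 21.2% quit rate that is about one quitter on placebo, too few to estimate an effect.

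Cost: a change of wording, with no new data, since race is already an analysis variable. The downside is a few degrees of freedom (more if there are more than two race groups, given the two time points) and an interaction standard error about 2-5% larger. Fixing the model now also avoids choosing it after the genotype results are known.

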### **4.2. Exclusion Criteria**

1. During the last 90 days from screening visit, meets any criteria for a DSM-IV diagnosis of drug or alcohol dependence—excluding tobacco or cannabis dependence and, for methadone or buprenorphine maintenance patients, opioid dependence—**AND** either evidences ongoing use of illicit drugs other than cannabis or continues to abuse or misuse prescription drugs such as CNS stimulants.
2. Pregnant with triplets or higher order multiples
3. Has an unstable psychiatric disorder (i.e., suicide risk moderate or severe, as reflected by a score of  $\geq 9$  on the MINI Section B (Suicidality) or a suicide attempt during the preceding year, psychiatric hospitalization within the last 3 months; current psychotic disorder based on the MINI)
4. Current or past Bipolar Disorder as determined by a study psychiatrist or psychologist based on assessment with the MINI, relevant information from the medical record and, when warranted, direct clinical evaluation.
5. Current, regular use of psychotropic medication, inhibitors of CYP2B6 (e.g., ticlopidine, clopidogrel), inducers of CYP2B6 (e.g., ritonavir, lopinavir, efavirenz), anticonvulsants (e.g., carbamazepine, phenobarbital, phenytoin), beta-blockers (e.g., metoprolol), Type 1C antiarrhythmics (e.g., propafenone and flecainide), drugs that require metabolic activation by CYP2D6 to be effective (e.g., tamoxifen), drugs that lower seizure

CONFIDENTIAL

- threshold (e.g., antipsychotics, tricyclic antidepressants, theophylline, or systemic corticosteroids), levodopa or amantadine

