### 5.1. Description

Bupropion for this study is supplied as commercial SR 150mg tablets. The placebo will be supplied as over-the-counter calcium carbonate 648mg tablets which are nearly identical in size, shape and color to the active bupropion product.

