### 5.3. Method for Assigning Participants to Treatment Groups

Participants will be randomly assigned to one of two treatment conditions: Bupropion 300 mg/day (n = 180) or placebo (n = 180). We will use small-block randomization by site (Penn or MATER) provided by [name], the study biostatistician. A PHQ-9 score of 10 or greater will be used to identify major depression and stratify the randomization on it. Study site (Penn or MATER) will be the second of the two stratification variables. Study staff and the Investigational Drug Service (IDS) staff will be responsible for medication randomization. The process for randomization is: 1) The research coordinator will complete a “randomization form,” which includes the variables to be entered into the randomization program and fax or email the form without protected health information to the UPenn site; 2) A designated study staff member

Table 1: Medication Dispensing Schedule

	Medication Dispensed For	Morning Dose	Evening Dose	Total Daily Dose
Visit A: Screening	N/A	No medication	No medication	
Visit B: Baseline	Wk 1	150 mg	No medication (for first 3 days); then 150 mg	150 mg
Visit C: Wk 1	Wk 2 through Wk 5	150 mg	150 mg	300 mg
Visit D: Wk 3	N/A	N/A	N/A	N/A
Visit E: Wk 5	Wk 6 through Wk 10	150 mg	150 mg	300 mg
Visit F: Wk 7		150 mg	150 mg	300 mg
Visit G: Wk 10	Endpoint	No medication	No medication	N/A

CONFIDENTIAL

This material is the property of the University of Pennsylvania. Do not disclose or use except as authorized in writing by the study sponsor

Visit H: Wk 24 Post-TQD	N/A	No medication	No medication	N/A
Visit I: 2 wk postpartum	N/A	No medication	No medication	N/A
Visit J: 6 wk postpartum	N/A	No medication	No medication	N/A

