## **9.5. Blood samples storage and retention.**

Blood for both the UPenn and Jefferson sites will be stored in a coded manner in a designated -80 degree freezer at UPenn and shipped to the laboratory of [name] at the University of Toronto, on dry ice approximately every four months or as necessary for the duration of the study. Samples will be shipped following the University of Pennsylvania's

CONFIDENTIAL

guidelines for shipping international biological samples. Samples will be coded and protected health information will not be included. DNA extraction and genotyping will be carried out in [name] laboratory. The nicotine metabolite ratio (NMR), a genetically informed biomarker based on the measurement of two long-lasting nicotine metabolites (cotinine and 3-hydroxycotinine), will also be measured. Finally, bupropion and hydroxybupropion plasma concentrations will be measured using blood obtained at the week-5 visit.

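### Plasma bupropion and hydroxybupropion cannot be tested as treatment interactions, because placebo women have no variation in drug level.

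*Combined protocol and SAP*

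**What the plan says.** Section 7.2.4 (Specific Aim 3) gives a single method for all its variables: "testing for moderation using the analytical models in Aim 1, testing for interactions with treatment". The effect of interest is the randomised contrast: "We will explore whether the risk of AEs and the efficacy of bupropion treatment (vs. placebo) is moderated by" a list of three groups of variables. The second group, described as the rate of bupropion metabolism, contains CYP2B6 variation and "plasma concentrations of bupropion and hydroxybupropion". The test is at alpha 0.05, "using the z-score for the interaction term for binary or continuous predictors", with a Wald chi-square for categorical predictors. The Study Summary and Section 2 carry the same list.

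Section 9.5 fixes the timing: "bupropion and hydroxybupropion plasma concentrations will be measured using blood obtained at the week-5 visit". Section 6.6 (Visit E) describes the same draw, two tubes (14 cc), without limiting it to one arm. On the content of the control tablet, Section 5.1 says: "The placebo will be supplied as over-the-counter calcium carbonate 648mg tablets".

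The levels appear in two other places that bear on their use. Section 7.2 correlates week-5 bupropion levels with self-report and pill counts. Section 1.1 says in general terms that the study will look at how concentrations, genotype and adherence affect cessation and adverse events. Neither gives an outcome model for the levels or restricts the analysis to the bupropion arm.

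**The concern.** A treatment-by-variable interaction compares the slope of outcome on the variable between the two arms. For drug concentration there is no placebo slope, because the placebo arm has no spread in concentration. The planned comparison therefore has nothing on one side.

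There is a second problem, one of interpretation. A moderator of a randomised effect should be fixed before treatment starts. The week-5 level is measured after randomisation and depends on whether the woman takes her tablets. Section 1.1 itself names adherence among the influences on concentration, and cites an earlier bupropion trial in which 42.9% of treated subjects were non-adherent. Reverse causation is also possible. Adverse events are recorded from week 1, and Section 3.2 allows them to lead to dose reduction or suspension, so an early event can lower the week-5 level. A woman who relapses early may also stop her tablets.

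At stake is whether a within-arm association that mixes exposure, adherence and early course is reported as evidence that drug level modifies the efficacy or safety of bupropion in pregnancy.

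**Working it through.** The plan states no figure for this analysis (Section 7.1 gives power only for the primary aims), so there is none to reproduce. The check is whether the stated model can be estimated.

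**Inputs**
- Arm sizes, Section 5.3: 180 bupropion, 180 placebo.
- Model, Section 7.2.4: Aim 1 model plus moderator and moderator-by-treatment term.
- Placebo content, Section 5.1: calcium carbonate.
- Other bupropion use: Section 4.2 excludes "Current, regular use of psychotropic medication" at entry.
- Assumption: bupropion-arm concentrations were drawn from a lognormal distribution to fill the column. The rank does not depend on this choice as long as the values vary.

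**Notation.** T = 1 for bupropion and 0 for placebo; C = concentration; W = 1 at 24 weeks and 0 at 10 weeks.

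**Single time point: columns 1, T, C, T×C**

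1. Placebo C = 0. In placebo rows T×C = 0 = C. In bupropion rows T×C = C. So T×C = C in all 360 rows: 4 columns, rank 3.
2. Placebo C = k, a constant below the assay limit. In every row C = k − kT + T×C (placebo: k − 0 + 0 = k; bupropion: k − k + C = C). The columns are again linearly dependent: 4 columns, rank 3.
3. Placebo C missing, complete cases only. Only the 180 bupropion rows remain, where T = 1 and T×C = C: 4 columns, rank 2. The treatment effect is lost as well.

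**Two-time-point form of the Aim 1 GEE: columns 1, T, W, T×W, C, C×T, C×W, C×T×W**

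With placebo C = 0, C×T = C and C×T×W = C×W. Two columns are redundant: 8 columns, rank 6.

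| Model | Columns | Rank |
|---|---|---|
| Placebo C = 0 | 4 | 3 |
| Placebo C = constant | 4 | 3 |
| Placebo C missing | 4 | 2 |
| Two-time-point GEE, placebo C = 0 | 8 | 6 |
| Bupropion arm only: 1, C | 2 | 2 |
| CYP2B6 genotype G: 1, T, G, T×G | 4 | 4 |

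The interaction is not identifiable under any treatment of the placebo values. The last two rows are the alternatives, and both can be estimated.

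**The case against.** The strongest reply is that the plan never writes the model out. If only arm and arm × concentration are entered, with placebo at zero and no separate concentration term, there are 3 columns (1, T, T×C) and rank 3, and software prints a z-score. Section 7.2.4 also allows categorical predictors, so exposure groups within bupropion could each be compared with placebo. Both points are correct. But the z-score from the reduced model tests the slope within the bupropion arm. It contains no comparison of slopes between arms, so calling it a treatment interaction gives it a meaning it does not have. Exposure groups compared with placebo set a group selected after randomisation against the whole control arm, and so give up the protection of randomisation.

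It can also be said that the exposure-response intention is already visible. Section 1.1 describes the earlier hydroxybupropion finding as coming from 154 treatment-adherent bupropion subjects, and Section 7.2 plans to control for compliance in the primary analyses. This shows that the right analysis is familiar to the study team and that part of the adjustment is planned. It does not replace the test that Section 7.2.4 specifies.

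Two qualifications stand. Placebo women may well be sampled at week 5, so the problem is absence of variation and not necessarily absence of a sample. And the aim is labelled hypothesis-generating, which limits the consequences.

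**Conclusion.** The concern holds. For plasma bupropion and hydroxybupropion the stated interaction test gives no result, and any coefficient that software does return is a non-randomised association within the bupropion arm. Two measures are affected, each for abstinence and for adverse events. NMR, CYP2A6, CYP2B6 genotype and the social and behavioural moderators exist in both arms and can be tested as written. The primary and secondary analyses, alpha and sample size are not touched.

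The conclusion rests on placebo concentrations being constant, which follows from the tablet content and the entry exclusion. An occasional stray placebo reading would break the exact collinearity but would still leave no usable placebo slope. Although the aim is exploratory, this should be corrected: the analysis in Section 7.2.4 is the only outcome model the plan gives for concentrations that require an extra blood draw, and leaving it unrepaired leaves the choice of model until after the data are seen.

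**What to change.** In Section 7.2.4, and in the matching text of the Study Summary and Section 2:

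- Remove plasma bupropion and hydroxybupropion from the list of treatment-interaction moderators.
- State that they will be analysed as exposure-response within the bupropion arm only, adjusted for baseline smoking, and reported as non-randomised association and not as moderation.
- Give results with and without adjustment for pill-count adherence. Adherence partly determines the level, so the two models answer different questions.
- For adverse events, relate the week-5 level to events recorded after the draw (the week 7 and week 10 assessments), so that earlier events which may have changed the level are not counted as its consequence.
- State how values below the assay limit and missing samples are handled.
- Keep CYP2B6 genotype, measured in both arms, as the treatment-interaction moderator for bupropion metabolism.

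The cost is a few sentences in an exploratory section. No visit, sample, data item or sample size changes.
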